4. TRIAL OBJECTIVES

4.1. Primary Aim:

The primary aim is to compare short- (1 year), mid- (3 years), and long-term (5 years) cumulative incidences of failures in participants who undergo a second aqueous shunt (SAS) to those cumulative incidences of failures in participants who undergo transscleral diode laser cyclophotocoagulation (TLC) for eyes with uncontrolled glaucoma with a single existing aqueous tube shunt implant.

The primary outcome variable is success or failure of treatment at 1, 3, and 5 years, where treatment failure is defined as meeting one or more of the following 4 criteria:

1. Intraocular pressure (IOP)
 - a) >18 mm Hg on maximum tolerated topical IOP-lowering medications, or
 - b) Reduction of < 20% IOP on maximum tolerated topical IOP-lowering medications from medicated preoperative IOP, or
 - c) \leq 5 mm Hg without IOP-lowering medicationson IOP confirmation visit, 6 months after initial study intervention; or
2. Reoperation for glaucoma; or
3. Addition of an oral CAI for the study eye on or after the 6-Month Study Visit; or
4. Loss of light perception vision (NLP).

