5. TRIAL DESIGN

This proposed study is a prospective, randomized, multicenter, masked, parallel group study. Sites will be selected based on surgeon's surgical qualifications and experience with the two study interventions, as well as on sufficient staffing and facility resources for conducting the study examinations. The participants will be randomly assigned to receive a SAS or undergo TLC. The cumulative incidences of treatment failure at 1, 3 and 5 years will be compared between groups.

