7.4. Sample Size Calculations

The definition of success/failure in this study is similar to the Ahmed versus Baerveldt Comparison (ABC) study.³ In the ABC study, the 1- and 5-year failure rate for the primary Baerveldt tube shunt group was 14% and 34%, respectively. Anticipated failure rate for the SAS group is 50% more than the primary tube shunt (~21%=14% x1.5 for 1 year, and 50% = 34%x1.5 for 5 years). Setting the power at 80% and alpha at 5%, a sample size of **91** participants in each group (182 total) would allow us to detect a difference of 20% or more reduction in cumulative incidence of failures in the TLC group from an anticipated 50% failure at 5 years in the SAS group (i.e. <30% in TLC vs 50% in SAS).

The retention rate in the ABC study was 65% at the 5-year visit. A total of **280** participants would allow for a 35% dropout rate (or deaths) during the 5-year study period.

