16. DATA ANALYSIS

16.1. *Interim Analysis/Safety Monitoring*

A number of interim analyses will be performed. The purpose of these analyses will be:

- a. To monitor recruitment targets in subgroups of interest (NVG vs non-NVG) and to monitor balance between treatment groups with regard to prognostic factors.
- b. To provide a regular mechanism for evaluating data quality, protocol adherence, and side-effect patterns including adverse reactions.
- c. To determine whether the study should be terminated early. Negative results could suggest that there is no possibility of ever establishing significance between-group differences.
- d. To assess the possibility that a positive but nonsignificant trend might require an increase in the originally projected sample size or an increase in the study duration.

Interim analyses will be performed every 3 months for the first year of enrollment and every 6 months thereafter. Interim analyses may also be performed at any time upon the request of the DSMB. The DCC will provide the results to the DSMB for making all decisions regarding the future conduct of the study. All investigators will be masked as to the results of interim analyses.

16.2. *Primary Analysis*

In the primary analysis, the null hypothesis is that there is no difference in one-year cumulative failure rates between the SAS group and the TLC group. The cumulative failure rates will be compared with Fisher exact test with one degree of freedom. The survival time from the treatment to failure will be estimated by Kaplan-Meier survival curve for each group and compared between the two treatment groups with the log-rank test. The potential effect of covariates will be assessed with the Cox proportional hazards models.

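### Section 16.2 states only a one-year primary null, while the trial is sized at 5 years; the 3- and 5-year test is unspecified and the stated 80% power does not belong to the stated test

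*Combined protocol and SAP*

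**What the plan says.** - **Section 16.2 (Primary Analysis).** It says that "the null hypothesis is that there is no difference in one-year cumulative failure rates" between the arms. The next sentence reads "The cumulative failure rates will be compared with Fisher exact test with one degree of freedom" and carries no time point of its own. Kaplan-Meier time to failure is then "compared between the two treatment groups with the log-rank test", and Cox models assess covariates. Years 3 and 5 are not mentioned.
- **Section 4.1 (Primary Aim).** The aim is to "compare short- (1 year), mid- (3 years), and long-term (5 years) cumulative incidences of failures". The primary outcome is success or failure at each of the three times.
- **Section 5 (Trial Design).** "The cumulative incidences of treatment failure at 1, 3 and 5 years will be compared between groups", with no test named.
- **Section 7.4 (Sample Size).** With 80% power and 5% alpha, 91 evaluable per arm are to detect a 20-point reduction "from an anticipated 50% failure at 5 years in the SAS group". SAS failure at one year is put at about 21%; no one-year TLC rate is given. The 280 "participants would allow for a 35% dropout rate (or deaths) during the 5-year study period".
- **Section 10.1.2, Table 1.** The Year 5 visit is ideally on day 1825. The preferred window is days 1735-1915 and the acceptable window days 1461-2007.

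**The concern.** The aim, the sample size and the analysis section point to different questions. The aim names three time points, the sizing uses the last, and the only written null uses the first. Three consequences follow.

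1. The 80% power in 7.4 is quoted for a comparison that 16.2 does not state. The comparison that 16.2 does state has no power calculation.
2. Fisher's test needs a yes/no status for each eye. Section 16.2 has no rule for eyes lost or dead while still successful. This matters little at one year, but at 5 years a third of eyes may be in that position, and the denominator could be chosen after the data are seen.
3. The one named test that handles censoring, log-rank, compares whole curves. If one arm fails early and the other late, it can miss a real difference in 5-year incidence, which is the quantity the trial was sized to detect.

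**Working it through.** **1. The plan's own figure.** Inputs from 7.4: 50% vs 30%, 80% power, alpha 5% (two-sided reproduces the plan's number; one-sided does not). With the unpooled normal approximation,

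n = [0.5×0.5 + 0.3×0.7] × (1.960 + 0.842)² / 0.20² = 0.46 × 7.849 / 0.04 = 90.3, rounded up to 91 per arm.

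Enrolment: 182 / 0.65 = 280. Both figures reproduce, and both belong to a 5-year comparison of two proportions.

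**2. Power of Fisher's test at 5 years.** Exact enumeration, 50% vs 30%:

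| Evaluable per arm (SAS/TLC) | Power |
|---|---|
| 91/91 | 0.750 |
| 90/92 | 0.763 |
| 92/90 | 0.776 |
| 102/102 | 0.806 |

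With 140 enrolled per arm and a random number of completers, power is about 0.77-0.78.

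**3. Power of Fisher's test for the one-year null.** SAS is 21% (7.4). The TLC rate must be assumed:
- Proportional hazards: HR = ln 0.70 / ln 0.50 = 0.515, so TLC = 1 − 0.79^0.515 = 11.4%.
- Same risk ratio as at 5 years: 30/50 = 0.6, so TLC = 0.6 × 21% = 12.6%.

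| Assumed TLC at 1 year | 140 per arm, no loss | 91 per arm |
|---|---|---|
| 11.4% | 0.53 | 0.35 |
| 12.6% | 0.41 | 0.26 |

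With loss at the assumed rate, the 11.4% case at 140 per arm gives 0.51-0.54, depending on the denominator. Power of 80% would need TLC failure of about 8.6% (140 per arm) or 6% (91 per arm).

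**4. Log-rank against a fixed-time test at 5 years.** Simulation settings:
- 140 per arm; SAS 21% at 1 year and 50% at 5; TLC 30% at 5.
- Piecewise-exponential failure with a rate change at 1 year.
- Independent exponential loss reaching 35% at 5 years, which implies 1 − 0.65^(1/5) = 8.3% at 1 year and 1 − 0.65^(3/5) = 22.8% at 3 years.

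The fixed-time test is z = [ln(−ln S₁) − ln(−ln S₂)] / √[G₁/(ln S₁)² + G₂/(ln S₂)²]. S is Kaplan-Meier survival at 5 years and G is the Greenwood sum of d/[n(n−d)].

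| Assumed TLC at 1 year | Log-rank | 5-year Kaplan-Meier |
|---|---|---|
| 11.4% (proportional hazards) | 0.90 | 0.88 |
| 18% | 0.78 | 0.88 |
| 21% | 0.73 | 0.89 |
| 25% | 0.62 | 0.89 |

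These figures treat failure as observed continuously.

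**5. Effect of the visit schedule.** Under proportional hazards, with failures seen only at the scheduled visits from Month 6 on:
- Visits exactly at nominal times: the 5-year estimates read 50%/30%, power 0.86.
- Visits spread uniformly over the preferred windows (an assumption), coded to nominal time: 50%/30%, power 0.82.
- The same visits coded by actual date: 46%/28%, power 0.76, because failures first seen after day 1825 drop out of the estimate.

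**6. What the denominator does if Fisher is carried forward.** Expected crude SAS rate under the settings of step 4:

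| Year | True | Lost successes dropped | Counted as successes | Completers only |
|---|---|---|---|---|
| 1 | 21% | 22% | 20% | 21% |
| 3 | 37% | 41% | 34% | 37% |
| 5 | 50% | 57% | 43% | 50% |

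With equal loss in both arms, Fisher's type I error is 0.036-0.044 for every denominator and year, and that of the Kaplan-Meier test is 0.048-0.051.

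**The case against.** **The Fisher sentence has no time limit.** Read with sections 4.1, 5 and 7.4, repeating it at 1, 3 and 5 years is a natural reading. This stands. A reader might infer that no 3- or 5-year comparison is planned at all; the documents do not support that, since section 5 promises one. What is missing is the hypothesis, the test and the denominator.

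**Censoring is already handled.** Kaplan-Meier, log-rank and Cox are planned, and under proportional hazards log-rank is slightly stronger than the fixed-time test (0.90 vs 0.88). This also stands. The log-rank weakness depends on early TLC rates of 18-25%, which no document gives. Section 3 cites one 47-eye retrospective study with earlier failures after cyclodestruction; that suggests a direction, not rates. If the curves separated early and converged by year 5, the 5-year test would be the weaker one; that case was not simulated. Choosing between whole-curve and fixed-time comparisons is partly a choice of estimand, but section 4.1 has already chosen incidence at fixed times.

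**Biased rates and false positives.** A reader might infer that the trial will report 57% or 43% where the truth is 50%, or that type I error is inflated. Neither follows. The biased readings need denominators that the plan does not adopt. The evaluable count of 91 after 35% dropout suggests completers only, which is unbiased under independent loss. Section 15 also asks sites to try to document the outcome of absent participants, although that is not an analysis rule. Type I inflation needs strongly unequal loss: at an assumed 45% vs 25%, Fisher at 5 years reaches 0.099, 0.089 or 0.041 for the three denominators in the order of the last table.

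**The 75% figure.** It is specific to exactly 91 vs 91, where Fisher's test is unusually discrete. The fair statement is 75-78%. The sample size arithmetic itself is not wrong.

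**Conclusion.** The point holds as a mismatch and an under-specification. The primary time point in 16.2 disagrees with 7.4, and the 3- and 5-year test and its denominator are not stated. The 80% power belongs neither to the one-year null (about 53% at a TLC rate of 11.4%, 41% at 12.6%, with 140 per arm and no loss) nor to Fisher's test at 5 years (about 75-78% on about 91 evaluable per arm). The 5-year shortfall is a few points; the one-year shortfall is large, but it rests on an assumed TLC rate.

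Log-rank is valid and the strongest choice under proportional hazards. It does not answer the 5-year incidence question, and its power would fall from about 0.90 to 0.78-0.62 under the assumed early-failure patterns. All simulated figures assume independent loss. Type I error is not a concern when loss is similar between arms. Crude-rate bias at 3 and 5 years arises only if lost successes are dropped or counted as successes. This should be settled before outcomes are compared by arm.

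**What to change.** 1. Make the primary time point in 16.2 agree with 7.4. If one year stays primary, give that null its own power calculation with a stated TLC rate.
2. At the primary time point, test the between-arm difference in Kaplan-Meier cumulative failure (Greenwood variance, complementary log-log scale). Report the difference with a 95% CI at 1, 3 and 5 years. Keep log-rank and Cox as supportive, and state the denominator wherever Fisher's test is kept.
3. Assign failures and censoring to nominal visit time, so that a failure first seen at a Year 5 visit after day 1825 counts in the 5-year estimate.
4. Restate power for the chosen test: about 75-78% for Fisher on about 91 evaluable per arm, or roughly 82-88% for the 5-year Kaplan-Meier test on 140 enrolled per arm with independent 35% loss and nominal visit coding, depending on visit timing.
5. Analyse eyes by assigned arm, report loss by arm with reasons, and add a sensitivity analysis for informative loss and death. Kaplan-Meier does not cure either.

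**Cost.** SAP wording and routine programming; no new data, visits or enrolment. The fixed-time test gives up about 2-3 points of power against log-rank if hazards are proportional, and it would have less power than log-rank if the curves separate early and converge by year 5.

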2. SUMMARY

| | |
|----------------------------------------------|----------------------------------------------------------------------------------------------------------------------------------------------------------------------------------------------------------------------------------------------------------------------------------------------------------------------------------------------------------------------------------------------------------------------------------------------------------------------------------------------------------------------------------------------------------------------------------------------------------------------------------------------------------------------------------------------------------------------------------------------|
| Study Objective | To compare the 1-, 3-, and 5-year outcomes of a second aqueous shunt (SAS) to Transscleral Diode Laser Cyclophotocoagulation (TLC) in eyes with uncontrolled glaucoma with a single existing aqueous tube shunt implant. |
| Study Endpoint (Failure) | 
 1. Intraocular pressure (IOP) 
 a. > 18 mmHg on maximum tolerated topical IOP-lowering medications, or b. reduced by < 20% on maximum tolerated topical IOP-lowering medications from medicated preoperative IOP, or c. ≤ 5 mmHg without glaucoma medications on IOP confirmation visit(s), 6 months after initial study intervention; or 2. Additional reoperation for glaucoma (enhancement procedures allowed in the first 4 months); or 3. Addition of an oral carbonic anhydrase inhibitor (CAI) for the study eye on or after the 6-month visit; or 4. No light perception (NLP) |
| Study Population | 18 to 85 years of age with uncontrolled glaucoma on maximum tolerated topical therapy with a single existing tube shunt implant |
| Study Design | Prospective, multicenter, randomized, masked, parallel group |
| Treatment Groups | 
 1. Second Aqueous Shunt Implant (SAS) 2. Transscleral Diode Laser Cyclophotocoagulation (TLC) |
| Duration of Participant Participation | 5 Years |
| Number of Study Visits | 10 – 13 visits |
| # of Evaluable Participants | 91 in each group (182 total) |
| Anticipated Maximum # of Participants | 280, allowing for a 35% dropout |
| Recruitment Period | 1 year |
| Study Centers | Up to 70 centers |
| Site Funding Available | No |
| IRB Submission | Site's responsibility (submission, questions, fees) |

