7.2. Randomization Scheme

An adaptive block randomization scheme will be implemented with a block size of 4 and balancing between NVG and non-NVG strata within each site.

Upon completion of the Screening/Baseline visit, the study eye will be randomly assigned to one of the 2 treatment groups: SAS or TLC within each stratum (NVG vs non-NVG) and each site based on the computer generated assignment.

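### The 80% power stated in 7.4 is not the power of the Fisher exact test that 16.2 names for cumulative failure; for 50% vs 30% with 91 per group that test has 75%.

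*Combined protocol and SAP*

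**What the plan says.** Section 7.4 sets the operating characteristics ("Setting the power at 80% and alpha at 5" percent) and the contrast ("i.e. <30% in TLC vs 50% in SAS", both at 5 years). It concludes that 91 "participants in each group (182 total) would allow us to detect a difference of 20% or more reduction in cumulative incidence of failures". The Summary repeats the evaluable number as "91 in each group (182 total"). Section 7.4 gives neither the formula nor the test behind the 91, and does not say whether the 5% is one- or two-sided.

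Section 16.2 states that "the null hypothesis is that there is no difference in one-year cumulative failure rates between the SAS group and the TLC group". It then gives the test for the proportions: "The cumulative failure rates will be compared with Fisher exact test with one degree of freedom". The same paragraph adds Kaplan-Meier curves compared by a log-rank test, and Cox models for covariates. It does not say which of Fisher and log-rank decides the primary comparison.

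**The concern.** A power statement belongs to a particular test. Fisher's exact test is conservative at moderate sample sizes: its true type I error stays below the nominal level, and power is lost with it. A sample size from a large-sample formula therefore does not give Fisher the same power. The wording of 16.2 raises the doubt directly, because a Fisher exact test has no degrees of freedom. Section 16.3.2 attaches the same phrase, correctly, to an asymptotic chi-square test.

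At stake is whether the 80% describes the analysis that will be run. There is also a practical risk: if the choice between Fisher and chi-square is left open until the data are in, it could decide a borderline result.

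**Working it through.** **Inputs.** From 7.4: failure 50% (SAS) and 30% (TLC) at 5 years, alpha 5%, power 80%, 91 evaluable per group, 35% loss. Equal allocation follows from the equal group sizes and the blocks of 4 in 7.2. Assumption: two-sided testing, taken from the no-difference null in 16.2.

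**Step 1. Reproduce the plan's figures.** Normal approximation with unpooled variance:

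n = (1.96 + 0.8416)² × (0.5×0.5 + 0.3×0.7) / 0.20² = 7.849 × 0.46 / 0.04 = 90.3, rounded up to **91**.

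This matches exactly. The pooled-variance formula gives 93 and the continuity-corrected formula 103. One-sided sizing gives 74, or 83 with continuity correction, so a one-sided reading does not explain the 91. Enrolment: 182 / 0.65 = **280**, which also matches.

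**Step 2. Power of the tests at 91 per group, 50% vs 30%.** For the tests of proportions, all 92 × 92 possible outcomes were enumerated, each weighted by Binomial(91, 0.5) × Binomial(91, 0.3), and the weights of outcomes with two-sided p ≤ 0.05 were summed.

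| Test | Power | Largest true size at nominal 5% |
|---|---|---|
| Fisher exact | 75.0% | 3.7% |
| Pearson chi-square, uncorrected | 79.4% | 5.2% |
| Chi-square with Yates correction | 75.0% | not computed |
| Boschloo | 78.3% | at most 5% by construction |

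**Step 3. Sample size at which Fisher reaches 80%.** 101 per group gives 79.9% and 102 gives 80.6%. That is 204 evaluable, or 204 / 0.65 ≈ 314 enrolled at the plan's 35% loss.

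**Step 4. The log-rank test in 16.2.** Assume proportional hazards and every evaluable participant followed to failure or 5 years.

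- Hazard ratio = ln(0.70) / ln(0.50) = 0.515.
- Expected failures = 91 × 0.50 + 91 × 0.30 = 72.8.
- Schoenfeld: |ln 0.515| × √72.8 / 2 = 2.83; 2.83 − 1.96 = 0.87; power ≈ **81%**.

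**Step 5. Sensitivity to the planning rates.** Section 7.4 rounds 34% × 1.5 = 51% to 50%. With 91 per group, Fisher has 79.0% at 51% vs 30%, 79.6% at 50% vs 29%, and 74.4% at 51% vs 31%. The gap is about what a one-point change in the assumed difference moves.

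**The case against.** The strongest reply is that 7.4 never ties its 80% to Fisher, and that 16.2 also commits to a log-rank test with about 81% power at the same size. This stands. A reader might infer that the trial runs a 25% risk of missing the planned effect. That would be true only if Fisher alone decided the comparison at 5 years, and 16.2 does not say so.

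A reader might also infer that the sample size calculation is wrong. It is not: 91 and 280 both reproduce. What is missing is the link to a named test. That 91 came from the unpooled formula is a well-supported inference, not something the plan states.

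The null in 16.2 concerns one-year rates, whereas 50% and 30% are 5-year rates, so 75% is Fisher's power for the contrast in 7.4 and not for the null as worded. This too stands, but it does not rescue the 80%. For one year the plan gives only the SAS rate, about 21%. If the same 40% relative reduction held (an assumption: 21% vs 12.6%), Fisher's power would be about 26% with 91 per group. That mismatch needs its own correction.

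Two smaller replies also carry weight. The gap is comparable to rounding in the planning rates (step 5). And preferring Fisher is legitimate, since it guarantees error control, while Pearson's size can slightly exceed 5%. A reader might take chi-square or Boschloo as restoring the planned power; at 79.4% and 78.3% neither quite reaches 80%.

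**Conclusion.** The inconsistency is real and modest. The only test that 16.2 names for cumulative failure proportions has 75.0% power at 91 per group for 50% vs 30%, five points below the 80% in 7.4. This assumes a two-sided 5% test, 91 evaluable per group and the 5-year planning rates. The shortfall is specific to Fisher: it nearly disappears if an uncorrected chi-square was meant, and disappears if the log-rank test is primary and hazards are proportional. The documents do not support a claim that the trial as a whole is underpowered by this amount, or that more participants must be enrolled. They do show a stated power attached to no test, and a named test described in terms that belong to another.

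**What to change.** In 16.2, state which test is primary for the 5-year contrast on which 7.4 is sized. If Fisher is kept, delete the degree-of-freedom phrase.

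In 7.4, name that test and state its power at 91 per group, 50% vs 30%, two-sided 5%:

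- Fisher: 75%.
- Uncorrected chi-square: about 79%.
- Log-rank: say that the 80% refers to this test under proportional hazards.

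Which test to choose is partly preference; stating the power that goes with it is not. The choice should be fixed before outcome data are seen.

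The cost is one sentence in 16.2 and one in 7.4, and possibly a slightly less favourable stated power. No extra enrolment is needed. The one-year null in 16.2 remains to be reconciled with the 5-year sizing separately.

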16.3. Secondary Analysis

16.3.1. To compare changes in vision related to quality of life from baseline to 1-, 3-, and 5-year visits between SAS and TLC groups, measured by NEIVFQ-25

Differences between study groups in NEI-Visual Function Questionnaire (NEI-VFQ-25) and its subscales will be analyzed both cross-sectionally and longitudinally. Either a Student's t-test or a nonparametric Wilcoxon rank sum test will be used for the cross-sectional comparison between groups and a mixed-effect model with repeated measurements will be used to compare two groups over the study period.

16.3.2. To compare cumulative incidence of vision-threatening complications at 1, 3, and 5 years post-treatment between groups

Vision-threatening complications will be defined by the DSMB. The safety effect of treatment will be assessed by comparing the cumulative proportions of vision-threatening complications or the event rates per person-year from the time of randomization with asymptotic χ^2 test with one degree of freedom. The survival curve from the time of randomization to the first occurrence of vision-threatening events will be compared between the two randomization groups with the log-rank test. The potential effect of covariates will be assessed with the Cox proportional hazards models.

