4.2. Secondary Aims

The secondary aims are to compare safety (i.e. complications, loss of best-corrected visual acuity [BCVA], and pain) and vision-related quality of life between the two treatments, including:

1. Cumulative incidence of vision-threatening complications at 1, 3, and 5 years after initial study intervention;
2. BCVA at scheduled visits after the 6-month postoperative visit. Changes of BCVA from baseline and the incidence of eyes that have lost more than 2 lines of BCVA will be compared between groups at each visit.
3. Incidence and severity of pain at the 1-week and 1-month postoperative visits.
4. Total number of visits during the first 3 months, first year, and over 5 years.
5. Changes in vision-related quality of life from baseline to 1-, 3-, and 5-year visits, assessed by the NEI VFQ-25.

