15. WITHDRAWAL OF STUDY PARTICIPANT

If a participant wishes to withdraw from the study, the reason for withdrawal should be documented in the source document and REDCap. An exit visit should be performed if possible. If a participant does not return for a scheduled visit, every effort should be made to contact the participant and document the participant's outcome.

Relevant tests and assessments should be performed according to the schedule for Year 5/Exit visit if withdrawal occurs between surgery and Year 5 visits.

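### The visit-by-visit VFQ-25 and BCVA comparisons rest on tests of whoever has a value at that visit; take them instead from the mixed model already planned

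*Combined protocol and SAP*

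**What the plan says.** **Aims.** Section 4.2 lists "Changes in vision-related quality of life from baseline to 1-, 3-, and 5-year visits, assessed by the NEI VFQ-25" and "BCVA at scheduled visits after the 6-month postoperative visit". It asks for change in BCVA, and loss of more than two lines, to be compared at each visit. Under Table 2 the BCVA visits after Month 6 are Month 12 and Years 2, 3 and 5.

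**Methods.** Sections 16.3.1 and 16.3.3 both state that group differences "will be analyzed both cross-sectionally and longitudinally". For a single visit, "Either a Student's t-test or a nonparametric Wilcoxon rank sum test will be used for the cross-sectional comparison between groups". The sentence then continues: "a mixed-effect model with repeated measurements will be used to compare two groups over the study period". For BCVA there is also a Fisher exact test of loss of more than two lines at each follow-up visit. Neither approach is named as the main one. No analysis population, missing-data method or sensitivity analysis is given for these outcomes.

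**Expected loss.** Section 7.4 notes "The retention rate in the ABC study was 65% at the 5-year visit" and sizes the trial so that 280 participants "would allow for a 35% dropout rate (or deaths) during the 5-year study period".

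**Exit visits.** Section 15 says "Relevant tests and assessments should be performed according to the schedule for Year 5/Exit visit if withdrawal occurs between surgery and Year 5 visits". Table 2 has one column for Year 5 and exit, which includes VFQ-25 and visual acuity. Table 1 gives Year 5 its own acceptable window, days 1461-2007.

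**The concern.** A t-test or Wilcoxon test at Year 5 drops everyone without a Year 5 value, including what they contributed at baseline, Year 1 and Year 3. That costs precision. It also sets the randomised groups aside in favour of the groups that stayed. If people leave because of how the eye is doing, and do so differently after a second shunt than after laser, the Year 5 comparison can move in either direction.

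A mixed model fitted to all visits uses the earlier values and is much less exposed to this, but the plan does not say that it will supply the visit contrasts. If the two methods disagree at Year 5, nothing says which one answers the aim. Section 3 says that no quality-of-life data exist for these interventions in this setting, so these secondary results will be read closely.

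**Working it through.** **1. The plan's own figures.** Two proportions, 0.50 against 0.30, two-sided 5% (sidedness assumed), 80% power, unpooled variance:

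n = (1.960 + 0.842)² × (0.50×0.50 + 0.30×0.70) / 0.20² = 7.85 × 0.46 / 0.04 = 90.3, so 91 per group.

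182 / 0.65 = 280 enrolled. Loss: 0.35 × 280 = 98. Left at Year 5: 182, or 91 per group. These figures size the failure endpoint. The documents give no SD, effect size or power for VFQ-25 or BCVA, so everything below rests on assumed values.

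**2. What is planned at a single visit.**

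| Outcome | Visits in the aim | Named for a single visit | Mixed model |
|---|---|---|---|
| VFQ-25 | Years 1, 3, 5 | t-test or Wilcoxon | yes, across follow-up as a whole |
| BCVA | Month 12, Years 2, 3, 5 | t-test or Wilcoxon | yes, across follow-up as a whole |
| BCVA loss of more than 2 lines | each follow-up visit | Fisher exact | none |

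**3. Precision on change from baseline.** Assume SD 18 and correlation 0.7 between visits. SD of change = 18 × √(2 × 0.3) = 13.9. SE with 91 per group = 13.9 × √(2/91) = 2.07. A simulation (140 per arm, about 65% retained at Year 5, 3000 runs) with dropout unrelated to outcome gave 2.03 for attenders only and 1.93 for likelihood using all visits. The ratio is 2.03 / 1.93 = 1.05.

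**4. Bias on change from baseline.** Same simulation, true Year 5 difference 5 points:

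| Why participants leave | Attenders only | All visits, likelihood |
|---|---|---|
| Unrelated to outcome | 4.97 | 4.98 |
| Last observed change, both arms | 4.75 | 5.02 |
| Last observed change, one arm only (odds ×1.65 per 10-point worsening) | 3.50 | 4.98 |

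The one-arm bias is 3.50 - 5.00 = -1.5 points, or 1.5 / 2.03 = 0.74 SE. Repeat simulations gave 3.55 against 4.91 and 3.57 against 5.05. Allowing dropout straight after baseline reduced the bias to about -1.2. Letting one-arm leaving depend on the last value instead of the last change reversed the sign, to about +0.5 to +0.7. These cases put the dependence in the arm with the smaller change; by symmetry, putting it in the other arm turns the sign over. For dependence in both arms, a repeat gave 4.97, so that bias is near zero.

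**5. Year 5 values instead of change.** Section 4.2 speaks of change, but Sections 16.3.1 and 16.3.3 speak of group differences in the measures, so raw values might be tested. Second illustration: no true difference, SD 1, correlation 0.9 per year, mean decline 0.1, 0.3 and 0.5 SD at Years 1, 3 and 5, dropout driven by the last observed value.

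| Dropout | Bias, Year 5 value | Bias, change |
|---|---|---|
| 35% in each arm, same mechanism | about 0 | about 0 |
| 30% against 40% | about 0.07 SD | about 0.01 SD |
| 25% against 45% | about 0.14 SD | about 0.01 SD |
| 35% in each arm, value-related in one only | about 0.24 SD | about 0.02 SD |

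The all-visit likelihood estimate stayed within 0.01 SD of zero throughout. With 91 per group the test statistic shifts by bias × √(91/2). A bias of 0.10 SD shifts it by 0.67 and raises a 5% error to about 10%; 0.25 SD shifts it by 1.69 and raises it to about 39%.

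**6. Exit values.** A withdrawal at month 8 (about day 243) yields VFQ-25 and BCVA values on the combined Year 5 and exit schedule. Table 1 places day 243 in the Month 6 window (days 121-273). The plan does not say which label applies in the analysis.

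**The case against.** The strongest reply is that a likelihood-based model is already in the plan, in the very sentence that names the t-test. A reader who stops at the first half might infer that the comparisons are only t-tests or Wilcoxon tests. The documents do not support that: both sections plan a longitudinal analysis as well. What stands is narrower. The model is not said to give visit-specific differences, and it is not named as the main analysis.

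A reader might also infer that early exit values will be analysed as Year 5 data. Section 15 and the shared column in Table 2 say what to collect at exit, not how to analyse it, and Table 1 limits Year 5 to days 1461-2007. This is an unwritten assignment rule. Its possible size is also easy to overstate. If 25-75% of the 98 leavers had an exit visit (assumed), exit records would make up 24.5/206.5 to 73.5/255.5, or 12-29%, of the combined column. If exits were spread evenly over 1825 days, 365/1825 = 20% of them would fall on or after day 1461 and count as Year 5, leaving 0.8 × 12% to 0.8 × 29%, about 9-23%. The 98 also include deaths, and exit visits are requested only where possible.

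Finally, the bias depends on the mechanism chosen and vanishes when dropout is alike in both arms. That is correct, and it limits the point to a risk. The precision gain does not need outcome-related dropout.

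**Conclusion.** The point holds as a cheap improvement. The visit-specific aims rest on tests of attenders, although a better method is already planned and its data are already collected.

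- **Precision.** The Year 5 standard error on change is about 5% larger than it need be (assumed SD 18, correlation 0.7, 65% retained).
- **Bias.** Possible, not established. It is about -1.5 to +0.7 points on change for a true difference of 5 under one-arm dependence, with the sign depending on mechanism and arm, and near zero if dropout is alike in both arms. Raw Year 5 values are more exposed than change if dropout depends on the last value.
- **Limits.** The 35% is an allowance at Year 5 drawn from another trial. The documents give no loss figure for Years 1, 2 or 3, so they do not support a claim of bias at those visits. They also do not support the reading that the Year 5 result will be biased.

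These are secondary outcomes; the primary failure analysis is not affected.

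**What to change.** **Main change, Sections 16.3.1 and 16.3.3.** State that the main analysis is the treatment difference at each visit in the aim, taken from the planned mixed model: VFQ-25 at Years 1, 3 and 5; BCVA at Month 12 and Years 2, 3 and 5. Specify visit as a category, a treatment-by-visit interaction, baseline included, and all randomised participants with any measurement. Keep the t-test or Wilcoxon as supportive; the Wilcoxon is also a useful check because acuity down to hand motion is eligible and may be far from normal. The Fisher test of line loss can stay, with its denominator shown by arm and visit.

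**Clarification on exit values.** Count an exit evaluation as Year 5 only if it falls on days 1461-2007. Place an earlier one in the Table 1 window containing its actual day where that outcome has a scheduled visit. Otherwise use it only in a supportive analysis with continuous time: a month-8 VFQ-25 value, for example, falls in the Month 6 window, where no VFQ-25 is scheduled.

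**Cost and downside.** SAP wording and a little programming; no new data. The model assumes data missing at random given earlier values, so add a sensitivity analysis for dropout not at random and report deaths by arm.
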